**Figure 1: Study Flow Diagram**

Abbreviation: EOS- End of study

Prior to Protocol R475-OA-1611 Amendment 4 Global, patients were randomized 3:3:3:3:1 to receive one of the following treatment regimens:

- Fasinumab 1 mg Q4W - Fasinumab 1 mg SC Q4W and naproxen-matching placebo oral, twice daily
- Fasinumab 3 mg Q4W - Fasinumab 3 mg SC Q4W and naproxen-matching placebo oral, twice daily
- Fasinumab 6 mg Q8W - Fasinumab 6 mg SC Q8W (patients received placebo injections at the study visits where study drug was not administered) and naproxen-matching placebo oral, twice daily

- Naproxen - Fasinumab-matching placebo SC Q4W and naproxen 500 mg oral, twice daily
- Placebo - Fasinumab-matching placebo SC Q4W and naproxen-matching placebo oral, twice daily

A total of 285 patients were enrolled in the fasinumab 3 mg SC Q4W and fasinumab 6 mg SC Q8W groups. However, dosing in these patients was discontinued, as recommended by the independent Data Monitoring Committee (DMC) in April 2018.

Post Protocol R475-OA-1611 Amendment 5 Global approximately 2,560 patients were planned to be randomized 3:3:3:1 to receive:

- Fasinumab 1 mg Q4W - Fasinumab 1 mg SC Q4W and naproxen-matching placebo oral, twice daily
- Fasinumab 1 mg Q8W - Fasinumab 1 mg SC Q8W (patients received placebo injections at the study visits where study drug was not administered) and naproxen-matching placebo oral, twice daily
- Naproxen - Fasinumab-matching placebo SC Q4W and naproxen 500 mg oral, twice daily
- Placebo - Fasinumab-matching placebo SC Q4W and naproxen-matching placebo oral, twice daily

Randomization was stratified according to the affected index joint (hip or knee), the K-L score (2 to 3, or 4) at the screening visit, and geographical region (Europe, North America, and Rest of the World [South Africa]).

Protocol R475-OA-1611 Amendment 6 provided patients the option to continue in the study and receive treatment for an additional year (Year 2). The treatment arm the patients were assigned in Year 2 was determined by the treatment arm they were randomized to in Year 1 according to the following rules:

- Patients randomized to receive Placebo or Naproxen in Year 1 will be assigned to receive Naproxen prn during Year 2
- Patients randomized to received Fasinumab 1 mg Q4W in Year 1 will be assigned to remain on this dose for Year 2
- Patients randomized to received Fasinumab 1 mg Q8W in Year 1 will be assigned to remain on this dose for Year 2

## 2.2. Sample Size and Power Considerations

In this study, approximately 2560 patients were planned to be randomized to fasinumab 1 mg SC Q4W (840), fasinumab 1 mg SC Q8W (600), naproxen (840), or placebo (280) (see Section 5.1.3 of the protocol). This sample size was expected to provide adequate power for the comparisons between fasinumab and naproxen at week 16 for the WOMAC pain and physical function scores and the Patient Global Assessment - Osteoarthritis (PGA-OA) score and provide long term data for safety assessment.

The sample size was based on results of the WOMAC pain and physical function subscale scores and the PGA from the R475-PN-1227 study. The calculation of sample size assumed a 2-sided alpha level of 0.025 and a 15% dropout rate up to week 16 and a 30% dropout rate up to week 52. Enrollment of 840 patients in the fasinumab 1 mg Q4W group and 280 patients in the placebo group would have provided at least 99% power to detect an effect size of 0.46 in the WOMAC pain and physical function subscale scores (i.e., an absolute treatment difference of 1.1 between fasinumab and placebo and a standard deviation [SD] of 2.4 at week 16 and 52 for the full analysis set [FAS]). This sample size would have provided 99 % power to detect an effect size of 0.36 in PGA for an absolute treatment difference of 0.4 with a SD of 1.1 at week 16, and 98% power at week 52 for the FAS.

For the fasinumab 1 mg Q8W group, the 600 patients would have been compared to the approximately 200 patients in the placebo group who were enrolled after Protocol R475-OA-1611 Amendment 5 Global was implemented. For such comparisons, 2-sided alpha level of 0.025 and a 15% dropout rate up to week 16 and a 30% dropout rate up to week 52 were assumed. Additionally, the effect size for such comparisons were assumed to be 80% of the effect size for the comparison between fasinumab 1 mg Q4W group and the placebo group. Under these assumptions, enrollment of 600 patients in the fasinumab 1 mg Q8W group and 200 patients from the placebo group would have provided 97% power to detect an effect size of 0.368 ( $=0.46*80%$ ) in the WOMAC pain and physical function subscale scores at week 16 and 93% power at week 52. This sample size would have provided 84% power to detect an effect size of 0.288 ( $=0.36*80%$ ) in PGA at week 16, and 75% power at week 52 for the full analysis set (FAS).

The sample size calculation was also based on previously reported results of the WOMAC pain subscale and physical function subscale and the PGA for naproxen (Ekman 2014) (Schnitzer 2015). Assuming a 2-sided alpha level of 0.025 and a 15% dropout rate up to week 16 and a 30% dropout rate up to week 52, an enrollment of 840 patients in the fasinumab 1 mg Q4W group and the naproxen group would have provided at least 97% power to detect an effect size of 0.22 in the WOMAC pain subscale (i.e., an absolute treatment difference of 0.51 with a SD of 2.3) at week 16, and 92% power at week 52 for FAS. This sample size would have provide 98% power to detect an effect size of 0.24 in WOMAC physical function subscale (i.e., absolute treatment difference of 0.50 with a SD of 2.1) at week 16, and 96% power at week 52 for FAS. This sample size would have provided 87% power to detect an effect size of 0.18 in PGA at week 16 between fasinumab 1 mg Q4W and naproxen for the FAS.

While the number of patients randomized was based on the sample size calculations in the protocol, the analyses of the primary and secondary efficacy endpoints will be performed at levels of significance as specified in Section 5.7.4 of this document which differs than the initial assumptions used above.

Due to regional irregularities noted in a parallel phase 3 study, the population for the primary and secondary efficacy analyses was changed in Protocol Amendment 8 Global to be performed on a modified Full Analysis Set (mFAS) that excludes patients in the randomization stratum for that region. Based on the number of patients randomized and the testing strategy specified in Section 5.7.4 it is estimated that this mFAS will provide:

- 99.9% power to detect a statistically significant difference between the 1 mg Q4W group and the placebo group in the WOMAC pain and physical function subscales at Week 16 using an alpha level of 0.05.
- 42% and 46% power to detect a statistically significant difference between the 1 mg Q8W group and the placebo group in WOMAC pain and physical function subscales, respectively, at Week 16 using an alpha level of 0.01.
- 99.9% power to detect a statistically significant difference between the 1 mg Q4W group and the naproxen group in the WOMAC pain and physical function subscales at Week 16 using an alpha level of 0.04.

As the analysis for Year 2 will be descriptive only, a targeted sample size based on power considerations was not implemented for Year 2.

### **2.3. Study Plan**

Study assessments and procedures are presented by study period and visit in Section 10.2 Table 3 and Table 4. A schedule for follow-up on JR surgery during the study is presented in Section 10.2 Table 5.

### **3. ANALYSIS POPULATIONS**

In accordance with guidance from the International Conference of Harmonization of Technical Requirements for Registration of Pharmaceuticals for Human Use (ICH) guideline ICH E9 Statistical Principles for Clinical Trials (ICH, 1998), the following populations of analysis will be used for all statistical analysis:

#### **3.1. The Full Analysis Set (FAS)**

The FAS includes all randomized patients excluding patients affected by the urgent safety measure (i.e. patients randomized to the 3 mg Q4W or 6 mg Q8W doses) and is based on the treatment allocated (as randomized). Efficacy and patient reported outcome endpoints for Year 1 will be analyzed using the FAS including patients randomized to fasinumab 1 mg Q4W, fasinumab 1 mg Q8W, naproxen and placebo. For the analyses of fasinumab 1 mg Q8W group comparing to the control groups, only patients concurrently randomized (i.e. after Protocol R475-OA-1611 Amendment 5 Global was implemented) will be included.

#### **3.2. The Modified Full Analysis Set (mFAS)**

Due to regional irregularities noted in a parallel phase 3 study that became fully apparent only after unblinding that study, and the concern that the same irregularities would be present in data from similar sites from the same region in this study, the primary and secondary efficacy analyses will be performed on a modified Full Analysis Set (mFAS). This mFAS is comprised of the FAS excluding patients from the region of concern (Rest of the World stratum). Efficacy and patient reported outcome endpoints will be analyzed using the mFAS including patients randomized to fasinumab 1 mg Q4W, fasinumab 1 mg Q8W, naproxen and placebo. For the analysis of fasinumab 1 mg Q8W group comparing to the control groups, only the subset of patients concurrently randomized (ie, after Protocol R475-OA-1611 Amendment 5 Global was implemented) will be included.

#### **3.3. The Per Protocol Set (PPS)**

The per protocol set (PPS) includes all randomized patients from the mFAS who received all protocol required doses during the 16-week treatment period for the week 16 analysis and who do not have to be excluded due to relevant protocol violations. The PPS will be used to perform sensitivity analyses for the primary and selected secondary endpoints. Section 10.4 contains the list of protocol violations which lead to exclusion from the PPS and corresponding protocol deviation identification number (PDID). For the analysis of fasinumab 1 mg Q8W group comparing to the control groups, only the subset of patients concurrently randomized (i.e. after Protocol R475-OA-1611 Amendment 5 Global was implemented) will be included.

A PPS using the entire FAS is defined analogously to above and will be used for performing sensitivity analysis on the entire FAS.

#### **3.4. The Safety Analysis Sets (SAF)**

The Year 1 safety analysis set (SAF – Year 1) includes all randomized patients from the FAS who received any study drug; it is based on the treatment received (as treated). Treatment compliance/administration and all clinical safety variables for Year 1 will be analyzed using the

SAF – Year 1 including patients randomized to fasinumab 1 mg Q4W, fasinumab 1 mg Q8W, naproxen, and placebo.

The Year 2 safety analysis set (SAF – Year 2) includes all patients who received at least 1 dose of the Year 2 study drug; it is based on the treatment received during Year 2 (as treated). Treatment compliance/administration, all clinical efficacy and safety variables and all patient reported outcomes from Year 2 will be analyzed using the SAF – Year 2.

The following rules will be used to define the actual treatment a patient received:

- Patients randomized to either the placebo or naproxen arm who receive at least one dose of active fasinumab during Year X will be considered as treated with fasinumab 1 mg Q8W and classified in the fasinumab 1 mg Q8W treatment arm for the purpose of analysis using the SAF – Year X, where X = 1 or 2.
- Patients randomized to the placebo arm who have not received any active fasinumab injections but were ever dispensed active naproxen during Year 1 will be considered as treated with naproxen and classified in the naproxen treatment arm for the purpose of analysis using the SAF – Year 1.
- For patients randomized to either the fasinumab 1 mg Q8W or Q4W arms, as treated is defined to be as randomized and they will be classified in the treatment arm they were randomized to for the purpose of the analysis using the SAF – Year X, where X = 1 or 2, with the following exceptions:
  - In Year 1, if a patient receives no doses of active naproxen or fasinumab, then the patient will be considered as treated with placebo and classified in the placebo treatment arm for the purpose of analysis using the SAF – Year 1.
  - In Year 1, if a patient receives no doses of fasinumab but were ever dispensed any active dose of naproxen, then the patient will be considered as treated with naproxen and classified in the naproxen treatment arm for the purpose of analysis using the SAF – Year 1.
  - In Year 2, if a patient receives no doses of fasinumab, then the patient will be considered as treated with naproxen prn and classified in the naproxen prn treatment arm for the purpose of analysis using the SAF – Year 2.

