#### Treatment Period for Year 2 (Week 52E to Week 104E)

Study weeks during Year 2 will be denoted with an E to represent study weeks during the extension (eg, week 52E) and to differentiate them from study weeks with the same numbers in the follow-up period for patients who only participate in Year 1.

Eligible patients who choose to participate in Year 2 will not be re-randomized at week 52. Patients will receive treatment based on the treatment they received in Year 1, as shown below.

Year 1	Year 2
Fasinumab 1 mg SC Q4W and naproxen-matching placebo oral, twice daily	Fasinumab 1 mg SC Q4W and naproxen-matching placebo oral, prn*
Fasinumab 1 mg SC Q8W (patients will receive placebo injections at the study visits where study drug is not administered) and naproxen-matching placebo oral, twice daily	Fasinumab 1 mg SC Q8W (patients will receive placebo injections at the study visits where study drug is not administered) and naproxen-matching placebo oral, prn*
Fasinumab-matching placebo SC Q4W and naproxen 500 mg oral, twice daily	Fasinumab-matching placebo SC Q4W and naproxen 500 mg oral, prn*
Fasinumab-matching placebo SC Q4W and naproxen-matching placebo oral, twice daily	Fasinumab-matching placebo SC Q4W and naproxen 500 mg oral, prn*

\*The maximum naproxen dose (or naproxen placebo dose) allowed will be no more than the amount allowed during Year 1 (ie, 500 mg twice daily or 1 capsule of placebo twice daily).

Naproxen (and naproxen-matching placebo) will be administered as needed (ie, prn) in Year 2 instead of twice daily as in Year 1, due to the known safety profile associated with chronic NSAID use.

A fasinumab-matching placebo/naproxen-matching placebo group will not be included in Year 2 so as not to have patients who are experiencing moderate-to-severe pain due to their OA go for an entire 2-year period with only rescue medication of acetaminophen/paracetamol available to them for pain control. Patients who were randomized to fasinumab-matching placebo/naproxen-matching placebo in Year 1 will be switched to fasinumab-matching placebo/naproxen 500 mg prn for the second year of treatment to ensure they have access to some form of pain medication in addition to acetaminophen/paracetamol.

During the treatment period of Year 2 (week 52E through week 104E), rescue medication (acetaminophen/paracetamol) will continue to be permitted for all patients and use will be recorded in a diary.

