Note: Any Year 1 patient attending their week 52 visit on or after 26 March 2020 will no longer have the option to enroll into Year 2.

- 1. Completed the treatment period of Year 1
- 2. Did not permanently discontinue study drug during Year 1
- 3. Received no less than 10 of the 13 planned doses of SC study drug during the treatment period of Year 1
- 4. Provide informed consent for Year 2
- 5. Willing to continue to maintain current activity and exercise levels throughout Year 2
- 6. Willing and able to comply with clinic visits and study-related procedures and willing to provide follow-up information related to any JR surgery that occurs within the period of time covered by their intended participation in the study

#### 6.2.4. Exclusion Criteria for Year 2

Women of childbearing potential who are unwilling to continue to practice highly effective contraception during the study, and for at least 20 weeks after the last dose. Highly effective contraceptive measures include stable use of combined (estrogen and progestogen-containing) hormonal contraception (oral, intravaginal, transdermal) or progestogen-only hormonal contraception (oral, injectable, implantable) associated with inhibition of ovulation initiated 2 or more menstrual cycles prior to screening; intrauterine device (IUD); intrauterine hormone-releasing system (IUS); bilateral tubal ligation; vasectomized partner; and or sexual abstinence†‡.

† Sexual abstinence is considered a highly effective method only if defined as refraining from heterosexual intercourse during the entire period of risk associated with the study

treatments. The reliability of sexual abstinence needs to be evaluated in relation to the duration of the clinical trial and the preferred and usual lifestyle of the subject.

‡ Periodic abstinence (calendar, symptothermal, and post-ovulation methods), withdrawal (coitus interruptus), spermicides only, and lactational amenorrhea method (LAM) are not acceptable methods of contraception. Female condom and male condom should not be used together.

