#### 7. STUDY TREATMENTS

## 7.1. Investigational and Reference Treatments

Study drug in this study includes fasinumab, naproxen, and their matching placebo. Fasinumab and its matching placebo are SC study drug. Naproxen and its matching placebo are oral study drug.

Fasinumab drug product is supplied for this study in the following concentrations:

- Fasinumab 2 mg/mL: Each 1 mL single use pre-filled syringe delivers 0.5 mL of a 2 mg/mL solution (1 mg dose) of study drug
- Fasinumab-matching placebo: Each 1 mL single use pre-filled syringe delivers 0.5 mL of placebo solution

Naproxen 500 mg capsules and naproxen-matching placebo capsules will be provided by the sponsor.

#### Year 1

At the baseline visit of Year 1, patients will be randomized 3:3:3:1 to receive 1 of the following treatment regimens:

- Fasinumab 1 mg SC Q4W and naproxen-matching placebo oral, twice daily
- Fasinumab 1 mg SC Q8W (patients will receive placebo injections at the study visits where study drug is not administered) and naproxen-matching placebo oral, twice daily
- Fasinumab-matching placebo SC Q4W and naproxen 500 mg oral, twice daily
- Fasinumab-matching placebo SC Q4W and naproxen-matching placebo oral, twice daily

All patients will receive SC injections of fasinumab or fasinumab-matching placebo. All SC injections will be in the abdomen, thigh, or upper arm. Patients will be observed in the clinic for approximately 1 hour after study drug is administered. Patients randomized to earlier versions of the protocol with 3 mg Q4W or 6 mg Q8W fasinumab were discontinued from study drug for the remainder of the study and moved directly into the follow-up period.

Naproxen 500 mg or naproxen-matching placebo will be administered orally, twice daily. A proton pump inhibitor or other gastric protective medication may be prescribed if deemed medically necessary by the investigator or sub-investigator.

Doses of SC study drug must be given within  $\pm 7$  days from the scheduled dose date. If the window is missed, the SC dose of fasinumab or fasinumab-matching placebo should not be administered, however the oral dose of naproxen or naproxen-matching placebo will be dispensed. The next SC dose of fasinumab or fasinumab-matching placebo should be administered at the next scheduled dosing date.

Detailed instructions for study drug dose administration are provided in the pharmacy manual.

Year 2

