#### 7.3.2.2. Reasons for Temporary Discontinuation of Study Drug

Study drug may be temporarily discontinued due to medical need, as determined by the investigator. Subcutaneous study drug (fasinumab or fasinumab-matching placebo) will be temporarily withheld while awaiting imaging adjudication for worsening joint pain or when routine imaging suggests adjudicated arthropathy and prompts the need for additional imaging (see Section 9.6.1.1), or for patients who are determined to have orthostatic hypotension or determined to have new or worsening symptoms suggestive of sympathetic nervous system dysfunction while awaiting evaluation by a specialist (see Section 9.6.1.2). Patients may continue to take naproxen or naproxen-matching placebo during this time. Subcutaneous study drug (fasinumab or fasinumab-matching placebo) should not be re-started until the next study visit unless imaging/evaluation results are available within the current visit window. If oral study drug is temporarily discontinued by the investigator, patients may continue to take SC study drug during this time.

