- 10. Samples will be analyzed by the central laboratory and results evaluated by the investigator.
- 11. In the event of a positive urine pregnancy test result, the patient should have a serum pregnancy test with a negative result in order to continue study drug. If the serum pregnancy test is positive, the patient should be withdrawn from study drug and should be asked to return to the clinic for all remaining study visits per the visit schedule (see Section 8.2.3.11).
- 12. Collection of samples for PK, ADA, high-sensitivity C-reactive protein (hs-CRP), and research are mandatory at the time points specified above. In addition, PK, ADA, hs-CRP, and research samples may be drawn at any scheduled visit or unscheduled visit if a patient experiences a treatment-related

- safety TEAE. Samples should be collected prior to SC study drug administration on SC study drug dosing days.
- 13. Research samples should be collected after an overnight (minimum 8 hours) fast.
- 14. The purpose of this phone contact is to ask the patient if they have had or are scheduled (or on a waiting list) to have a JR. Pre-operative images should be submitted to the central reader for adjudication, if available.
- 15. Patients who end treatment early but agree to follow/continue to attend regular study visits do not complete the assessments associated with EOT/week 104E at the time they end treatment. Instead, they complete assessments associated with the study visit they are attending at the time they end treatment early.
- 16. If the affected joint has undergone JR, an X-ray may be substituted for an MRI.
- 17. The week 52E Year 2 visit should occur on the same day as the week 52 Year 1 visit, but could occur at any time during the visit window.

**Table 3:** Follow-up Period for Patients Undergoing Joint Replacement Surgery on Study

	Post-Operative	Long-Term
	Follow-up Visit 1	Follow-up Visit 2
	4 weeks after joint replacement surgery	20 weeks after joint replacement surgery
Follow-up Study Day (Visit Window) 	Follow-up Day 29 (±5)	Follow-up Day 140 (±7)
Treatment:		
Concomitant medications and therapy	X	X
Safety:		
Adverse events		→
Vital signs	X	X
Orthostatic blood pressure 	X	X
Physical examination with joint exam	X	X
Medical history related to the joint replacement	X	X
Joint pain questionnaire	X	X
Post-operative questionnaire 	X	X
Bilateral X-rays (shoulders, hips, knees) 	X 	X

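### The Year 2 safety set can label a fasinumab-randomized patient naproxen prn although that patient was assigned only placebo capsules and normally had fasinumab in Year 1

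*SAP*

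**What the plan says.** - **Who is in the set.** By SAP 3.4, SAF – Year 2 "includes all patients who received at least 1 dose of the Year 2 study drug", grouped by the treatment received in Year 2. Protocol 7.1 defines the term: "Study drug in this study includes fasinumab, naproxen, and their matching placebo". One placebo injection or one placebo capsule is therefore enough for entry.
- **How fasinumab-randomized patients are grouped.** SAP 3.4 keeps them as randomized, with exceptions. In Year 1, a patient with no fasinumab goes to naproxen only if active naproxen was ever dispensed, and goes to placebo if neither active drug was received. In Year 2 there is a single condition: "In Year 2, if a patient receives no doses of fasinumab, then the patient will be considered as treated with naproxen prn".
- **What they are assigned in Year 2.** The tables in the Protocol synopsis and in 7.1 give both fasinumab arms naproxen-matching placebo prn. For Q8W, "patients will receive placebo injections at the study visits where study drug is not administered". Neither document names the active visits.
- **Who may enter Year 2.** Protocol 6.2.3 requires: "Received no less than 10 of the 13 planned doses of SC study drug during the treatment period of Year 1"; and: "Did not permanently discontinue study drug during Year 1".
- **Timing.** Protocol Table 1 schedules bilateral X-rays at Week 52, and footnote 17 of 8.1.2 says: "The week 52E Year 2 visit should occur on the same day as the week 52 Year 1 visit". Protocol 7.3.2.2 withholds SC drug while imaging adjudication is pending, but of the oral drug it says: "Patients may continue to take naproxen or naproxen-matching placebo during this time".

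**The concern.** The reassigned patient was not assigned naproxen in Year 2, and the rule looks only at Year 2 injections, so it ignores the fasinumab received over the preceding year. The label thus describes neither the Year 2 drug nor the earlier exposure. The Year 1 exceptions in the same list show that the authors knew how to require dispensed naproxen, so the Year 2 wording looks like a drafting gap.

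What is at stake is the comparison in secondary objective 5: safety of fasinumab against naproxen up to 104 weeks, with adjudicated arthropathy (AA) as the central risk. Suspected AA is itself a reason to withhold SC drug, and confirmed AA is a reason to stop it. Patients who enter Year 2 and never get an active injection may therefore include a disproportionate share of joint cases. Each such case is taken from the fasinumab column and added to the comparator.

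**Working it through.** **1. Year 1 exposure.** Protocol Table 1 schedules SC injections at Weeks 0, 4, ..., 48. That is 48/4 + 1 = 13, which reproduces the 13 planned doses in Protocol 6.2.3. An entrant has had at least 10. If doses were given as assigned, a Q4W patient has at least 10 active doses. On a Q8W grid starting at Week 0, the active visits are Weeks 0, 8, ..., 48 (7 active, 6 placebo), so a Q8W patient has at least 10 − 6 = 4 active doses.

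**2. Year 2 grid for Q8W.** Protocol Table 2 schedules injections at 52E, 56E, ..., 100E, again 13. There are two readings:
- Alternation continues unbroken: active at 56E, 64E, 72E, 80E, 88E and 96E (6), placebo at 52E, 60E, ..., 100E (7). Week 52E is placebo.
- The sequence restarts at Year 2 entry: 52E is active, 4 weeks after the active Week 48 dose.

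The first reading fits an 8-week interval and the Protocol 3.2.1 statement that the regimen carries on unchanged. It is still derived, because the documents do not state it.

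**3. Who the rule catches.**
- *Route A, either fasinumab arm.* SC drug is withheld from 52E, the patient takes placebo capsules, and no active Year 2 injection is ever given. A temporary hold does not breach the Year 2 entry criteria, and those criteria do not require the Week 52 X-ray to have been read. This route needs no assumption about the Q8W grid.
- *Route B, Q8W only, on the unbroken grid.* The patient gets the 52E placebo injection and then stops before 56E, or misses 56E and every later active visit.

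**4. Size of Route B.** Year 2 numbers and dropout are not given. Assume that the Year 1 planning dropout (Protocol 10.2) applies with constant hazard. The chance of stopping in one 4-week interval is 1 − (1 − d)^(4/T):
- d = 30%, T = 52 weeks: 1 − 0.70^(1/13) = 2.7%
- d = 15%, T = 16 weeks: 1 − 0.85^(1/4) = 4.0%

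That is about 3 to 4 per 100 Q8W entrants. The naproxen prn group is formed from the Year 1 naproxen and placebo arms, so the 3:3:3:1 allocation with equal uptake gives 3 Q8W to 4 comparator patients. With stopping probability h, the reassigned share of the naproxen prn column is 3h/(4 + 3h):

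| h (assumed) | per 100 Q8W entrants | share of naproxen prn column |
|---|---|---|
| 1% | 1.0 | 0.7% |
| 2.7% | 2.7 | 2.0% |
| 4.0% | 4.0 | 2.9% |
| 10% | 10.0 | 7.0% |

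Missing a run of active visits adds little unless misses are frequent. If each is missed independently with probability m, the chance of missing 56E, 64E and 72E is m³: 0.1% for m = 10% and 2.7% for m = 30%.

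**5. The August 2020 stop.** The last possible entry date was 25 March 2020 (Protocol 6.2.3), and dosing stopped on 17 August 2020, 145 days later. The nominal 56E, 64E and 72E visits fall 28, 84 and 140 days after entry. The programme stop does not by itself create these patients.

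**6. Direction.** Let a/n be the event proportion in a fasinumab arm and b/N that in the comparator. Moving m patients, k of them with events, gives (a − k)/(n − m) and (b + k)/(N + m). The fasinumab proportion falls if k/m > a/n, and the comparator proportion rises if k/m > b/N. Both conditions hold if the reassigned patients are enriched for joint events.

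**7. Which tables (SAP 5, 5.8.7 and 10.1).**
- Affected: Year 2 on-treatment and post-treatment summaries on SAF – Year 2, and the SAF – Year 2 version of the combined Year 1 and 2 tables. In that version the patient's Year 1 events on fasinumab would also appear under naproxen prn.
- Not affected: SAF – Year 1 tables, the combined tables on SAF – Year 1 (the only set that Protocol 10.4.4 names for that period), and the joint replacement Kaplan-Meier curves, which use the Year 1 randomized group.

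**The case against.** The strongest reply is about timing. The Week 52 X-ray is a Year 1 procedure, and the SC injection is the last procedure at a dosing visit. For patients who continue, SAP 5 runs the Year 1 on-treatment period up to the first Year 2 dose. An AA dated to that X-ray may therefore be a Year 1 event, counted on SAF – Year 1 in the fasinumab arm. This stands as far as it goes. The SAP does not say whether AA is dated by imaging or by adjudication, and later joint events, the Year 2 post-treatment tables and the SAF – Year 2 combined tables stay exposed.

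Route A has a gap of its own. The SAP ends the Year 2 on-treatment period 4 weeks after the last Year 2 SC dose, and a patient on capsules alone has no such date. Which Year 2 table would hold that patient's events is unclear. The Protocol's version counts from the last study drug dose and does not have this gap.

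Other points also narrow the matter. Year 2 has no placebo group, so the authors may simply have had nowhere else to put the patient. The AA and destructive arthropathy Cox models compare with placebo, so the naproxen prn column does not enter them. Year 2 is descriptive. The SAP lists patients not treated as randomized, which gives partial disclosure.

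A reader might infer that the Q8W schedule makes this reassignment routine because 52E is always a placebo injection. The documents do not support that: the content of the 52E injection is an inference, and even on that inference the next injection is active.

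**Conclusion.** The rule is wrong as written. It places fasinumab-randomized patients under a drug that they were not assigned, and it disregards Year 1 fasinumab exposure. The wording of SAP 3.4 and the Year 2 treatment table are enough to show this.

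Its reach is limited. The number affected is probably small and cannot be taken from the documents. The figure of about 3 to 4 per 100 Q8W entrants rests on unbroken Q8W alternation and on Year 1 planning dropout carrying over to patients who have already completed a year. Route A cannot be quantified. The effect is confined to summaries on SAF – Year 2.

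A reader might go further and conclude that the order of the fasinumab and naproxen AA rates would reverse. No Year 2 counts or AA rates are given, so any such reversal would come from assumed numbers. What can be said is that the reassignment can be linked to the outcome, and that where it is, the error favours fasinumab in both columns at once. With a rare event, a few moved cases could matter.

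**What to change.** In SAP 3.4, replace the Year 2 exception as follows:
- A fasinumab-randomized patient who received any active fasinumab injection in Year 1 stays in the randomized fasinumab arm for SAF – Year 2.
- Naproxen prn is reserved for patients actually dispensed active naproxen.
- A footnote to each SAF – Year 2 safety table gives the number per fasinumab arm with no active Year 2 injection.

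It would also help to state which Year 2 visits carry the active Q8W injection, so that the footnote can be read correctly. This asks only that the existing schedule be written down.

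The cost is one sentence and one derivation, made before database lock. The downside is a few patients in the fasinumab column without an active Year 2 dose, which the footnote discloses.
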